8.4. AEs of Special Interest

When an AE of special interest specified in the trial protocol occurs, the investigator must fill out the "Report of Adverse Event of Special Interest for Hengrui Clinical Studies" and report to the sponsor within 24 hours of event awareness. If an AE of special interest is also an SAE, the "NMPA Serious Adverse Event Report Form" must also be completed.

- \geq Grade 3 infusion reaction
- \geq Grade 2 diarrhea/colitis, uveitis, interstitial pneumonia
- Other \geq Grade 3 immune-related AEs
- Any possible hepatic enzyme abnormalities (see 8.2.3, lacking other related causes of the abnormalities at the same time, e.g., PD, acute viral hepatitis, cholestasis, concomitant medication, previous concomitant liver disease, etc.)
- Grade 4 amylase or lipase elevation

When an AE of special interest specified in the trial protocol occurs, the investigator must fill out the "Report of Adverse Event of Special Interest for Hengrui Clinical Studies" and report to the sponsor within 24 hours of event awareness.

If an AE of special interest is also an SAE, the "NMPA Serious Adverse Event Report Form" must also be completed.

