11.5.4. Safety Analysis

Descriptive statistical analysis is primarily used to analyze the AEs, CTCAE Grade ≥ 3 , serious adverse events and adverse reactions, \geq Grade 3 adverse reactions, and AEs leading to dose modification in each population (the adverse reactions are defined as adverse events that are "definitely related, possibly related, and not assessable" to the investigational drug). Laboratory test results describe the baseline and the worse on-treatment value.

Besides, irAEs, including immune-related pneumonitis, immune-related enteritis, immune-related thyroid dysfunction, immune-related nephritis and renal failure, and immune-related hypophysitis, will be categorized and summarized using above summary analysis of AEs.

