### 5.5.2. Adverse events

All AEs are encoded by using MedDRA v24.0 and graded using NCI-CTCAE v4.03. For the same SOC and/or PT, multiple cases of the same events occurred in one subject will be counted only once. For the same AE reported in one subject multiple times but varying in CTCAE grade, the AE of the greatest grade will be enumerated.

Treatment-emergent adverse events (TEAEs) are defined as any adverse events (AEs) that are new or worse than those at baseline (before treatment) after initiation of the study drugs. Only TEAEs will be summarized, and all AEs will be listed.

Drug-related TEAE (ADR) is defined as TEAE having the causal relationship of "*treatment-related*" with study drugs. In this trial, the definition of "*treatment-related*" is as follows: It refers to the relationship with the study drugs: related, possibly related, and unassessable. If the relationship between the AE and the study drugs is missing, the AE will be considered as an ADR.

AEs will be ranked from high to low according to the proportion of SOC/Cluster occurrence (total populations receiving the treatment), from high to low according to the proportion of PT under SOC (total populations receiving the treatment), and in alphabetical order if the incidences of at least 2 PTs are equal. If there is no AE under an SOC/Cluster or PT, the analysis will not be performed. Refer to Appendices 4 and 5 for the definition of Cluster classification.

In AE summary table, AEs after study drug treatment are analyzed according to the population, and the frequency and proportion are used for statistical description. AEs will be summarized using descriptive statistics according to Hengrui's Statistical Analysis Reporting Standards, including but not limited to the following contents:

- Any TEAE
- Treatment-related TEAE
- Any TESAE
- Treatment-related TESAE
- Grade  $\geq 3$  TEAE according to CTCAE grading
- Grade  $\geq 3$  treatment-related TEAE according to CTCAE grading
- Any TEAE  $\geq 5\%$
- Treatment-related TEAE  $\geq 5\%$
- TEAE leading to SHR-1210 treatment discontinuation and interruption

- TEAE leading to apatinib treatment discontinuation, treatment interruption, and dose reduction
- TEAE leading to death
- TEAE of special interest (AESI, the preferred term for AE provided by medical monitor, see Appendix 2 for details; other Grade  $\geq 3$  immune-related adverse events (irAEs): meeting irAE definition requirements and Grade  $\geq 3$  according to CTCAE v4.03)

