- Immune-related TEAE (irAE, including two categories: 1) AE that the investigators determine to be related to SHR-1210 (including definitely related, possibly related, and indeterminable) and corrected with glucocorticoid drugs (except reactive capillary endothelial proliferation); 2) other irAEs that the investigators determine to be related to SHR-1210 without the use of glucocorticoids, with the preferred term for AE provided by medical monitor, see Appendix 3 for details)
- The selected TEAE (the preferred term for AE provided by medical monitor, see Appendix 4 for details)
- The selected TEAE that the investigators determine to be related to SHR-1210 (the preferred term for AE provided by medical monitor, see Appendix 5 for details) and glucocorticoid utilization rate
- No subject with TEAE leading to interruption, dose reduction, and termination of two drugs
- TEAE leading to treatment interruption (apatinib or SHR-1210)
- TEAE leading to treatment termination of two drugs

The incidence of AE is calculated based on the number of subjects having an AE, instead of the number of AE episodes.

AESIs include:

- Grade  $\geq 3$  infusion reaction
- Grade  $\geq 2$  diarrhea/colitis, uveitis, and interstitial pneumonia
- Other Grade  $\geq 3$  irAEs
- Liver enzyme abnormal event: ALT, AST, and total bilirubin (TBIL) are abnormal against baseline
- Grade 4 amylase or lipase increased
- Reactive capillary endothelial proliferation

Among them, the specific definition of liver enzyme abnormal events is as follows:

Baseline Period	Normal (AST/ALT and TBIL)	Abnormal (AST/ALT/TBIL)
Treatment Period	ALT or AST $\geq 3 \times \text{ULN}$ with TBIL $\geq 2 \times \text{ULN}$ and ALP $\leq 2 \times \text{ULN}$ and without hemolysis	AST or ALT $\geq 2 \times \text{baseline level}$ , and $\geq 3 \times \text{ULN}$ or AST or ALT $\geq 8 \times \text{ULN}$ with TBIL increase $\geq 1 \times \text{ULN}$ or TBIL $\geq 3 \times \text{ULN}$

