### List of Preferred Terms for Adverse Events of Special Interest

Event of Special Interest	Classification	Preferred Term of AE
Grade 4 amylase or lipase increased	Amylase	Amylase increased
Grade 4 amylase or lipase increased	Lipase	Lipase increased
Reactive capillary endothelial proliferation		Reactive capillary endothelial proliferation
Grade $\geq 3$ infusion reaction		Infusion related reaction
Grade $\geq 2$ diarrhea/colitis	Colitis	Immune-mediated enterocolitis
Grade $\geq 2$ diarrhea/colitis	Colitis	Colitis
Grade $\geq 2$ diarrhea/colitis	Diarrhea	Diarrhea
Grade $\geq 2$ uveitis		Eye pain
Grade $\geq 2$ interstitial pneumonia		Interstitial lung disease
Grade $\geq 2$ liver enzyme abnormal event		Hepatic enzyme abnormal

## Appendix 3

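### SAP Appendix 2 conflicts with the AESI definitions in SAP 5.5.2 for uveitis and liver events, and Appendix 3 omits non-endocrine irAEs not treated with glucocorticoids

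*SAP*

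**What the plan says.** SAP 5.5.2 includes this item in its list of AE summaries: "TEAE of special interest (AESI, the preferred term for AE provided by medical monitor, see Appendix 2 for details". The same section then says what the categories are. At Grade 2 or higher they include "diarrhea/colitis, uveitis, and interstitial pneumonia", matching Protocol 8.4 ("Grade 2 diarrhea/colitis, uveitis, interstitial pneumonia"). For the liver it gives "Liver enzyme abnormal event: ALT, AST, and total bilirubin (TBIL) are abnormal against baseline", and introduces a table of laboratory thresholds with "Among them, the specific definition of liver enzyme abnormal events is as follows". The table depends on baseline status. With normal baseline values it requires ALT or AST at least 3 times ULN with TBIL at least 2 times ULN, ALP no more than 2 times ULN, and no hemolysis.

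Appendix 2 has ten rows. The uveitis row holds one preferred term, *Eye pain*. The liver row holds one preferred term, "Hepatic enzyme abnormal", and its label adds a Grade 2 or higher condition.

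For irAEs, SAP 5.5.2 has two routes. The first takes any SHR-1210-related AE treated with glucocorticoids, whatever its term, except reactive capillary endothelial proliferation. The second covers "other irAEs that the investigators determine to be related to SHR-1210 without the use of glucocorticoids" and relies on the terms in Appendix 3. Protocol 11.5.4 promises a summary by type: "irAEs, including immune-related pneumonitis, immune-related enteritis, immune-related thyroid dysfunction, immune-related nephritis and renal failure, and immune-related hypophysitis, will be categorized and summarized".

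**The concern.** When a term list is the tool that finds an event, an error in the list becomes an error in the table. For uveitis, the listed term names a symptom and not the condition. For the liver event, the SAP holds two rules that select different subjects and does not rank them. For irAEs without steroids, the list reaches one organ system only.

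AESI and irAE rates are prominent safety results for a PD-1 antibody combination in patients with liver cancer. The liver thresholds also appear in Protocol 8.2.4 as grounds for SAE reporting unless the case is judged due to progression. A case reported as an SAE on those thresholds could therefore be absent from the AESI table that is meant to describe the same event.

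**Working it through.** No sample size, power or error rate is involved. The check sets the definitions beside the lists and counts terms.

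| Event | Definition (SAP 5.5.2) | How it is found | Match |
|---|---|---|---|
| Uveitis, Grade 2 or higher | Uveitis | *Eye pain* only (Appendix 2) | No |
| Liver enzyme event | ALT/AST, TBIL and ALP thresholds by baseline status | *Hepatic enzyme abnormal*, Grade 2 or higher (Appendix 2) | No |
| Interstitial pneumonia, Grade 2 or higher | Interstitial pneumonia | *Interstitial lung disease* only (Appendix 2) | Narrow |
| Amylase, lipase, infusion reaction, diarrhea/colitis, capillary proliferation | As named | Corresponding terms (Appendix 2) | Yes |
| irAE with glucocorticoids | SHR-1210-related | Any term, one exception | Yes |
| irAE without glucocorticoids | SHR-1210-related | 19 terms (Appendix 3) | Endocrine only |

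**Uveitis.** *Uveitis* is not a preferred term anywhere in Appendices 2 to 5. The row errs in both directions: an event coded *Uveitis* is not found, and Grade 2 eye pain of another origin is.

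**Liver event.** The SAP itself anticipates other liver labels: Appendix 4 lists 15 liver terms and Appendix 5 lists 11. Both include AST increased, ALT increased and blood bilirubin increased, none of which is in Appendix 2. Two cases show the conflict:

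- A subject with normal baseline values reaches ALT 3 times ULN with TBIL 2 times ULN, ALP no more than 2 times ULN and no hemolysis. The laboratory definition is met. If the site's events are coded as ALT increased and blood bilirubin increased, Appendix 2 does not find the subject.
- A subject with normal baseline values reaches ALT 3 times ULN (Grade 2 in the liver table of Protocol Appendix 4) with TBIL below 2 times ULN. If this is coded *Hepatic enzyme abnormal*, Appendix 2 counts the subject although the definition is not met.

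The planned laboratory shift tables (SAP 5.5.3) classify results as normal, or abnormal with or without clinical significance. They do not show enzymes and bilirubin crossing multiples of ULN together, so they do not recover the defined event.

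**irAEs without steroids.** Appendix 3: 19 of 19 terms are endocrine. Appendix 5: 11 liver + 5 skin + 3 digestive + 3 lung = 22 non-endocrine terms. Of the five irAE types named in Protocol 11.5.4, Appendix 3 has terms for two (thyroid dysfunction and hypophysitis) and none for pneumonitis, enteritis, or nephritis and renal failure. The protocol describes a steroid-free course for some of the missing events. Its Appendix 4 handles Grade 2 diarrhea/colitis and Grade 2 liver events by delaying treatment, and adds steroids only if the event lasts more than 5 to 7 days, relapses (bowel) or worsens. An SHR-1210-related event that settles on that course is not an irAE under the SAP.

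**The case against.** The strongest reply concerns irAEs. Appendix 3 governs only events without glucocorticoids. Protocol 9.1 gives high-dose hormone therapy from Grade 2 for pneumonitis (confirmed by CT), hepatitis, enteritis, nephritis and hypophysitis, and such events enter through the first route whatever their term. Protocol 9.1 also says that glucocorticoids do not apply to hypothyroidism, so a steroid-free list centred on endocrine terms has a visible rationale. This largely stands. It reduces the gap to events that resolve without steroids. It does not close the gap, because Protocol Appendix 4 describes a delay-first course for Grade 2 bowel and liver events. The protocol's two texts differ here and should be reconciled.

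A reader might infer that the AESI category of other Grade 3 or higher irAEs inherits a general undercount. The documents do not support that. At Grade 3 to 4, Protocol 9.1 and Appendix 4 start steroids directly for bowel and liver events, and 9.1 has lung, kidney and pituitary events treated too. Only a Grade 3 or higher event that received no glucocorticoid could be lost.

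A reader might also call the interstitial pneumonia row wrong, because *Pneumonitis* and *Immune-mediated lung disease* are absent. The listed term fits the named category, and Protocol 1.3.1 counts pneumonitis and interstitial lung disease separately. The row is narrow, not mistaken.

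Finally, the underlying events stay visible: all AEs are listed, the Appendix 4 and 5 clusters are tabulated, and liver cases reported as SAEs reach the SAE tables. This allows partial recovery. It does not make the AESI table correct, because separate term tables cannot show that enzyme and bilirubin criteria were met together.

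**Conclusion.** Two rows of Appendix 2, uveitis and liver, conflict with the definitions they are meant to implement. Applied as written, they can both miss and wrongly count subjects. Appendix 3 is incomplete, not wrong, and only for SHR-1210-related non-endocrine events without glucocorticoids.

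The size in terms is 2 of 10 Appendix 2 rows in conflict, 0 uveitis terms, 1 liver term against 15 in Appendix 4 and 11 in Appendix 5, and 19 of 19 Appendix 3 terms endocrine. These counts do not measure missed subjects. That number depends on how events were coded, which liver rule is programmed and who received steroids, none of which the documents show. It would therefore go too far to say that the counts will be wrong, or that the liver AESI table will be nearly empty. The supported statement is that they may be wrong. Efficacy analyses are not affected. The point deserves correction because the remedy is cheap and the outputs matter.

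**What to change.** 1. In Appendix 2, replace *Eye pain* with *Uveitis* in the uveitis row.
2. State that the laboratory table in SAP 5.5.2 governs the liver AESI. Screen candidates from the laboratory data without the term and grade filter, then apply documented medical review for hemolysis and for the other causes that Protocol 8.4 excludes: progression, acute viral hepatitis, cholestasis, concomitant medication and previous liver disease. A laboratory derivation alone cannot apply these conditions and could overstate the event in this population.
3. Extend Appendix 3 to the immune-specific non-endocrine terms already in Appendices 4 and 5, for example pneumonitis, immune-mediated lung disease, colitis, immune-mediated enterocolitis and immune-mediated hepatitis, or state why the list is restricted to endocrine terms. Adding every liver and bowel term would go too far. Protocol 9.1 requires other causes to be ruled out, and Protocol 1.3.1 warns that many diarrhea events may not be immune-related and that many patients with raised AST or ALT had liver cancer.

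The cost is a revision of the appendices (SAP version 2.0 already reissued Appendices 2 to 5), a clarifying sentence in 5.5.2, a re-run of the safety tables and some medical review. Reported AESI and irAE rates may change.

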9. MANAGEMENT OF ADVERSE EVENTS

9.1. Immune-Related Adverse Events (irAEs)

Immune-related adverse events (irAEs) are clinically significant side effects that are consistent with the immunological mechanisms of the investigational drugs. irAEs require further serological, immunological and pathological (biopsy) data to support its diagnosis. Also, tumors, infections, metabolism, toxins, or other pathogenic factors must be ruled out.

Management principles for immune-related adverse events (see Annex IV for details):

The treatment of irAEs should be based on the medical practice and guidelines of the study site. The treatment recommendations for irAEs are as follows. The details are shown in Annex IV for reference.

Subjects using hormones should pay attention to calcium and vitamin D3 supplement, acid suppression, and protection of gastric mucosa.

- **Immune-related pneumonitis**

In the clinical study of SHR-1210, the monitoring of signs and symptoms of immune-related pneumonitis, such as cough and chest discomfort, in the subjects will be strengthened.

A high-dose hormone therapy will be given to subjects with a Grade 2 and above event confirmed by chest CT. Subjects with a Grade 2 event can interrupt SHR-1210 and be treated, but subjects with a Grade 3 or 4 event should permanently discontinue SHR-1210. Consultation with the Department of Respiration is recommended.

For specific operations, refer to the followings:

Grade 2 event: 1 mg/kg/day of methylprednisolone or equivalent given via intravenous or oral administration. The changes in CT should be closely monitored. After the event recovers to Grade 1, oral administration of 0.5 mg/kg/day of prednisone is continued for 2 weeks, then the dose of prednisone is reduced by 5 mg/week until drug discontinuation.

Grade 3 event: 2-4 mg/kg/day of methylprednisolone or equivalent given via intravenous injection. The changes in CT should be closely monitored. After the event recovers to Grade 1, the dose of methylprednisolone is reduced by 50% every 3 days. Oral administration of 0.5 mg/kg/day of prednisone is continued for 2 weeks, then the dose of prednisone is reduced by 5 mg/week until drug discontinuation.

If the hormone therapy does not improve or deteriorate the condition after 3-5 days, a combination therapy with immunosuppressants can be used for the treatment after discussion with the sponsor.

- **Immune-related hepatitis**

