Grade 2 (Moderate)	Moderate reactions requiring treatment or interruption; rapidly resolve after symptomatic treatment (such as antihistamines, non-steroidal antiphlogistics, anesthetics, bronchodilators, intravenous fluids, etc.)	Intravenous administration of normal saline: 50 mg of diphenhydramine IV or equivalent and/or 325-1000 mg of acetaminophen; Bedside observation and close monitoring until recovery. Corticosteroids or bronchodilators can be considered based on clinical needs; The amount of investigational drug infused should be recorded in the original medical record; Pre-dose prophylactics are recommended for subsequent administrations: 50 mg of diphenhydramine or equivalent and/or 325-1000 mg of acetaminophen can be given at least 30 min before the administration of SHR-1210. Use corticosteroids (equivalent to 25 mg of hydrocortisone) when necessary.	Interruption. Re-administer at 50% of the initial rate after symptoms resolve. If no reaction occurs within 30 minutes, restore the original infusion rate (100%). Closely monitor. If the symptoms recur, the current SHR-1210 should be discontinued.
Grade \geq 3 (Severe)	Grade 3: Severe reaction without rapid recovery upon treatment and/or interruption; or symptoms recur after alleviation; or the subject develops sequelae that requires hospitalization. Grade 4 (Life-threatening)	Immediately discontinue SHR-1210; Intravenous administer normal saline. 
 Bronchodilators are recommended: subcutaneous injection of 0.2-1 mg of 1:1000 adrenaline solution or slow intravenous injection of 0.1-0.25 mg of 1:10000 adrenaline solution, and/or 50 mg of diphenhydramine plus 100 mg methylprednisolone or equivalent by intravenous injection if necessary; Based on the study site's guidelines for treating allergic reactions; Bedside observation and close monitoring until recovery.	Permanent discontinuation.

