9.3. Symptomatic Treatment for Apatinib-Related Adverse Reactions

1) Hand-and-foot syndrome (HFS)

HFS is a skin toxicity with palmar-plantar dysaesthesia or acral erythema and manifests especially in areas under pressure or force. It may occur in patients with tumor during chemotherapy or molecular targeted therapy. HFSR is characterized by numbness, dysesthesia, paraesthesia, tingling, no pain or pain, skin swelling, or erythema, desquamation, chapping, scleroma-like blisters, and severe pain.

HFS grading:

Grade 1: numbness/dysesthesia/paraesthesia, painless swelling or erythema of the hands and/or feet and/or discomforts that does not affect normal activities.

Grade 2: painful erythema and swelling of the hands and/or feet and/or discomforts affecting patients' activities of daily living.

Grade 3: wet desquamation, ulcers, blisters, or severe pain of hands and/or feet and/or severe discomforts that causes the patients to be unable to work or perform activities of daily living. Intense pain and loss of skin function, relatively rare.

Symptomatic treatment and management of HFS:

Some necessary symptomatic and supportive treatments must be taken, including: strengthen skin care, keep skin clean, and avoid secondary infections; avoid pressure or friction; use moisturizers or lubricants, topically use lotions or lubricants containing urea and corticosteroids; topically use antifungal or antibiotic treatment if necessary.

Note: If a HFS of Grade 3 or above occurs for more than 3 consecutive times with an aggravating trend, the subject should discontinue the study treatment and withdraw from the clinical study.

2) Hypertension

Patients should be strictly screened according to blood pressure requirements in the inclusion and exclusion criteria prior to enrollment. Patients with hypertension can control the blood pressure by adjusting the dose of or adding new antihypertensive drugs before administering the investigational drug. The blood pressure must be under 140/90 mmHg (average of 2 blood pressure measurements taken at least 24 h apart) before randomization.

Monitoring and handling of such hypertension: Blood pressure should be monitored at least 3 times a week during the first 2 cycles of the targeted pharmacological treatment.

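### The SAP's steroid-based irAE rule (5.5.2, category 1) has no route or aetiology limit: it can admit hand-foot syndrome, and it sorts infusion reactions by whether a steroid was given

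*SAP*

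**What the plan says.** SAP 5.5.2 defines an immune-related TEAE through two categories. The first is an "AE that the investigators determine to be related to SHR-1210 (including definitely related, possibly related, and indeterminable) and corrected with glucocorticoid drugs". One exception follows directly: "corrected with glucocorticoid drugs (except reactive capillary endothelial proliferation". The second category is "other irAEs that the investigators determine to be related to SHR-1210 without the use of glucocorticoids", restricted to the preferred terms in SAP Appendix 3. In the AESI line of the same section, other Grade ≥3 irAEs are identified as events "meeting irAE definition requirements" and reaching Grade 3 or higher.

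Protocol 9.1 describes irAEs as effects consistent with the drugs' immunological mechanism. It states that "irAEs require further serological, immunological and pathological (biopsy) data to support its diagnosis" and continues: "Also, tumors, infections, metabolism, toxins, or other pathogenic factors must be ruled out".

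The protocol also provides for corticosteroids in two settings outside 9.1. For hand-foot syndrome (9.3, the section on apatinib reactions) the supportive measures tell sites to "topically use lotions or lubricants containing urea and corticosteroids". For infusion reactions (9.2, Table 4) corticosteroids may be considered at Grade 2, and methylprednisolone may be given if necessary at Grade 3 or higher.

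**The concern.** Category 1 replaces a diagnosis with two data flags: a causality rating and a steroid record. In a combination trial the causality flag is wide, because possible and indeterminable both count as related. The steroid flag is also wide, because neither route nor cause is specified. The exception for reactive capillary endothelial proliferation shows that the authors already saw one kind of event the flags would wrongly admit, but they named only that one.

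At stake is the meaning of the irAE incidence, a main safety output for a PD-1 antibody and one that Protocol 11.5.4 requires to be summarised. If part of it is driven by skin toxicity of the partner drug, or by local habits in treating infusion reactions, it no longer measures what Protocol 9.1 defines.

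**Working it through.** No calculation applies. The documents state no irAE rate, and no design figure depends on the rule. The check sets the texts side by side and runs cases through the rule.

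**Requirements compared**

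| Requirement | Protocol 9.1 | SAP category 1 |
|---|---|---|
| Consistent with immune mechanism | Yes | Not stated |
| Supporting diagnostic data | Yes | Not stated |
| Other causes ruled out | Yes | Not stated |
| SHR-1210 causality | Not stated as a rating | Definite, possible or indeterminable |
| Steroid used to correct the event | Not part of the definition | Yes, any route |
| Named exceptions | None | Reactive capillary endothelial proliferation only |

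**How the protocol classes the two events.** Hand-foot syndrome is given as an example of an apatinib-related event in 5.3, sits under apatinib-related toxicities in Table 1, and is managed in 9.3. Infusion reactions have their own section (9.2) separate from irAEs (9.1), their own AESI line at Grade ≥3 (Protocol 8.4, SAP 5.5.2), and their own cluster, shared with hypersensitivity, in SAP Appendix 4. The irAE types listed in Protocol 11.5.4 name neither event, although that list is not worded as exhaustive. No hand-foot term appears in SAP Appendices 2 to 5.

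**Why category 2 does not even things out.** Every term in Appendix 3 is endocrine or glucose-related. An infusion reaction or hand-foot syndrome managed without a steroid therefore cannot enter through category 2.

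**Cases run literally**

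1. Hand-foot syndrome attributed to apatinib alone, topical corticosteroid used: the causality condition fails, so it is not counted.
2. Hand-foot syndrome rated possibly related or indeterminable to SHR-1210, corrected with a topical corticosteroid: both conditions are met, so it is counted. At Grade 3 it would also reach the class of other Grade ≥3 irAEs, if the irAE definition cited there is the SAP's own.
3. Case 2 without a steroid: not counted.
4. SHR-1210-related infusion reaction treated with a glucocorticoid: counted.
5. The same reaction treated without a glucocorticoid: not counted.
6. Reactive capillary endothelial proliferation treated with a glucocorticoid: not counted, by the named exception.

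Cases 4 and 5 differ only in the treatment given. Case 2 is admitted without anyone asking whether the mechanism was immune.

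**The case against.** The strongest reply is that the rule is narrower than it looks and that other outputs cover the gap.

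- **Attribution protects against hand-foot syndrome.** An investigator who follows the protocol's classification will attribute it to apatinib, and case 1 applies. This stands as a limit: misclassification is conditional, not automatic. It does not remove the problem, because possible or indeterminable causality is plausible when both drugs are given together.
- **The steroid must have corrected the event.** Premedication does not count. The Table 4 sentence "Use corticosteroids (equivalent to 25 mg of hydrocortisone) when necessary" concerns prophylaxis before later infusions, so it does not trigger the rule. This stands. Only steroids given to treat the reaction matter, and the protocol makes those conditional.
- **Infusion reactions may be partly immune.** Protocol 8.5 mentions them alongside acute immune-mediated reactions. This also stands: one cannot say that no infusion reaction meets 9.1. But steroid use does not identify which ones do.
- **Other outputs show the picture.** The SAP summarises selected SHR-1210-related events by organ cluster with steroid use (Appendix 5, which contains neither event), and it lists all AEs. Protocol 1.3.1 describes reported infusion reactions as infrequent and mild. The irAE summary is descriptive, with no test attached. This limits the consequence but leaves the headline irAE rate as defined.
- **Enforcing 9.1 in full could under-count.** The study schedule has no routine biopsy or immunology work-up for AEs, so requiring one could drop genuine irAEs. This stands and shapes the fix.

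A reader might also infer that a Grade 3 infusion reaction given a steroid is counted in two AESI classes. The documents do not establish this. The word other in the irAE line can be read as a residual class that excludes events already listed, and incidence is counted by subject, not by episode.

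**Conclusion.** The point holds as a defect in a stated classification rule. Category 1 departs from Protocol 9.1. It admits steroid-treated hand-foot syndrome when SHR-1210 attribution is at least possible or indeterminable, and it makes the irAE status of an SHR-1210-related infusion reaction depend only on whether a steroid was given. It does not affect the primary endpoint or any decision rule.

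The size cannot be derived. For hand-foot syndrome it would need three quantities the documents do not give: incidence, the share attributed to SHR-1210, and the share corrected with a corticosteroid. A reader might supply values. With assumed ranges of 20–40%, 25–50% and 25–50%, the product runs from 0.20 × 0.25 × 0.25 = 1.25% to 0.40 × 0.50 × 0.50 = 10%. That is 2.2 to 17.6 of the 176 patients (120 + 56) at the maximum planned size. All three ranges are assumptions. The product also overstates the effect on the overall rate, because a patient who has another irAE is already counted. It shows only how open the question is and should not be cited as an estimate of inflation.

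**What to change.** In SAP 5.5.2, category 1:

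1. Count only events corrected with systemic glucocorticoids.
2. Extend the existing exception to palmar-plantar erythrodysaesthesia and to infusion-related reaction/hypersensitivity. The latter two terms already have their own cluster in Appendix 4, and Grade ≥3 infusion reactions have their own AESI class.
3. Before database lock, have the medical monitor remove steroid-treated events with a documented non-immune cause. Do not make biopsy or immunology work-up a condition for keeping an event.
4. State that other Grade ≥3 irAEs excludes events already listed in another AESI class.

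These changes concern classification in the analysis only; patient management is unchanged. The cost is SAP wording and a short review of steroid-treated events. The reported irAE count will be slightly lower. Part of that reduction may be SHR-1210-related rash treated only topically, which would leave the irAE count; the main rash terms remain visible in the Appendix 5 skin cluster, where steroid use is reported.
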